## **4.4 Analysis of Secondary Efficacy Endpoints**

### **4.4.1 Progression-Free Survival**

Kaplan-Meier plots and descriptive statistics will be provided for PFS. Summary statistics will include lower and upper quartile and median PFS, PFS6 (Day 180) and PFS12 (Day 365).

Summaries of the number (%) of patients experiencing a PFS event (overall and also at Month 6 and Month 12) and the type of event (disease progression or death) will be provided.

All summary statistics will be presented with the appropriate 95% CI.

If necessary, a sensitivity analysis will be conducted to assess the potential impact of COVID-19 related deaths on PFS. That is, patients who had a PFS event due to death where the primary or secondary cause of death was COVID-19 infection or COVID-19 infection was reported as a fatal AE, will be censored at the last evaluable RECIST 1.1 assessment prior to COVID-19 infection related death.

### **4.4.2 Overall Survival**

The following numbers (%) of patients in the SAF will be presented at 12-month (Day 365) intervals and overall: those who have died, those still in survival follow-up, those lost to follow-up, those who withdrew consent, and those with censored OS.

Kaplan-Meier plots and descriptive statistics will be presented for OS. Summaries will include the lower and upper quartile and median OS and estimates of OS12 (Day 365).

All summary statistics will be presented with the appropriate 95% CI.

If necessary, a sensitivity analysis will be conducted to assess the potential impact of COVID-19 related deaths on OS. That is, patients who had a death event where the primary or secondary cause of death was COVID-19 infection or COVID-19 infection was reported as a fatal AE, will be censored at the date of their COVID-19 infection related death.

### **4.4.3 Objective Response Rate**

The ORR will be estimated for the SAF and will be presented with the corresponding exact 95% CIs.

The number (%) of patients with a confirmed response and the number (%) of patients with a single visit response (ie, an unconfirmed response) will also be presented.

Best objective response (BoR) will be summarised by n (%) for each category (CR, PR, SD, PD and NE).

### **4.4.4 Duration of Response**

A Kaplan-Meier plot and descriptive statistics will be provided for the DoR and the respective

Time to onset of first response for patients in the SAF who had responded to treatment (see Section 3.3.5). Summary statistics will include: lower and upper quartile and median DoR with appropriate 95% CIs.

#### **4.4.5 Time to Lung Cancer Mortality (NSCLC-Related Death)**

The following numbers (%) of patients in the SAF will be presented at 12-monthly intervals and overall: those with an NSCLC-related death, those still in survival follow-up, those lost to follow-up, those who withdrew consent, and those with censored time to lung-cancer mortality (separately for those who died from a cause not related to NSCLC and other reasons for censoring, as well as overall).

Kaplan-Meier plots and descriptive statistics will be presented for time to NSCLC-related mortality. Summaries will include the lower and upper quartile and median lung cancer mortality and estimates at Month12 (Day 365).

All summary statistics will be presented with the appropriate 95% CI.

### **4.5 Analysis of Secondary Safety Endpoints**

#### **4.5.1 Adverse Events**

All TEAEs reported up until 90 days following completion or discontinuation of durvalumab treatment or until the initiation of the first subsequent therapy (whichever occurs first) will be included in the summaries unless explicitly stated otherwise below.

All TEAEs will be summarised descriptively, in terms of number of patients (n) and percentage of patients (%) reporting the event by MedDRA SOC and PT.

Listings of AEs will include the date of onset, date of resolution (if AE is resolved) and investigator's assessment of severity, relationship to durvalumab, and NCI CTCAE Grade. Separate listings will be produced for all AEs, PRAEs, SAEs, AESIs, AEPIs, imAEs, AEs with outcome of death, AEs leading to discontinuation of durvalumab, AEs leading to discontinuation of study. Listings of AESIs, AEPIs and imAEs will also include the additional information (eg, intervention, dose, duration of therapy etc.) recorded for these AEs. All AEs that are not treatment-emergent will be flagged in the data listings and the time of onset will be flagged as 'pre-treatment', 'post-treatment and no other anti-cancer therapy' and 'after initiation of other anti-cancer therapy'.

An overall summary of AE data will be presented including the number and percentage of patients reporting the following:

- At least one AE
- At least one PRAE
- At least one AE of CTCAE Grade 3 or Grade 4
- At least one PRAE of CTCAE Grade 3 or Grade 4
- At least one SAE
- At least one Serious PRAE
- At least one AE leading to discontinuation of study treatment

- At least one PRAE leading to discontinuation of study treatment
- At least one AE leading to treatment interruption
- At least one PRAE leading to treatment interruption
- At least one AE with outcome of death
- At least one PRAE with outcome of death
- At least one AESI
- At least one AEPI
- At least one PRAE of special interest (AESI)
- At least one PRAE of possible interest (AEPI)
- At least one imAE
- At least one immune-mediated PRAE

The following summaries including the number and percent of patients by SOC and PT will be presented separately:

- All AEs / PRAEs
- All AEs / PRAEs of CTCAE Grade 3 or Grade 4
- All PRAEs of CTCAE Grade 3 or Grade 4 occurring within the six months of first dosed date
- All PRAEs which start within 90 days of last dose of durvalumab (irrespective of start of subsequent anti-cancer therapy)
- All AEs
  - This summary will include an AE event rate (per 100 patient years) for each PT. The number of patients with an AE in each PT is divided by the sum of the actual exposure to durvalumab (days) (see Section 0) over all patients. This is multiplied by 365.25 x 100 to create an event rate per 100 patient years.
- All AEs by maximum CTCAE Grade
- All AEs / PRAEs with outcome of death
- All SAEs / Serious PRAEs
- All AEs / PRAEs leading to discontinuation from durvalumab (Note: Reason for discontinuation recorded on the patient disposition page)
- All AEs / PRAEs leading to dose interruption/discontinuation of durvalumab (Note: Reason for discontinuation recorded on the patient disposition page)

A summary of most common AEs and another summary of most common AEs with CTCAE Grade 3 or higher, including all events that occur in at least 2.5% of patients overall will be presented by PT, by decreasing frequency. This cut-off may be modified after review of the data. The raw percentage will be compared to the cut-off, without applying any rounding to the percentage value (ie, a TEAE with frequency of 2.4% will not appear in the table if a cut-off is 2.5%).

A summary of deaths will be provided with the following information:

- Number of deaths (NSCLC-related, non-related, and unknown)
  - Number of deaths during the on-treatment study period up until 90-day follow-up

- and prior to initiation of first subsequent therapy
- Number of deaths occurring more than 90 days after the discontinuation of durvalumab or after initiation of first subsequent therapy

Listings of key patient information for Deaths and SAEs will be provided.

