4.2 Scientific rationale for study design

4.2.1 Rationale for safety endpoints

This study is designed to evaluate the safety of durvalumab monotherapy, using a fixed-dosing regimen, in unresectable Stage III NSCLC patients who are ineligible for chemotherapy and who have not progressed following radiation therapy. This study is designed to complement and expand the safety database from the ongoing Phase III PACIFIC Study and PACIFIC-5 Study (NCT03706690) and the ongoing Phase II PACIFIC-6 Study (NCT03693300). Given the potential for radiotherapy to increase the likelihood of anti-PD-L1-mediated pneumonitis, a need for additional safety data on the use of durvalumab under this context exists, including in the sub-population of WHO/ECOG PS 2 patients, who have not been representatively included in pivotal studies.

In the PACIFIC Study, the majority of imAEs with durvalumab occurred during the first 6 months of treatment (see the current version of the durvalumab IB). This timing is consistent with published literature using anti-PD-1 or anti-CTLA-4 agents, which indicates that most of the imAEs occur within 3 to 6 months of the initiation of treatment (Topalian et al 2012, Weber et al 2017). This study will assess the safety of durvalumab within the first 6 months of treatment as defined by Grade 3 and Grade 4 PRAEs, including the evaluation of the nature of toxicities (SAEs, AEs, Adverse Events of Special Interest [AESIs], imAEs), interventions and treatment, and outcome of treatment.

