7.3 Withdrawal from the study

Patients are free to withdraw from the study at any time (treatment and assessments) without prejudice to further treatment.

Patients who withdraw consent for further participation in the study will not receive any further durvalumab or further study observation, with the exception of follow-up for survival, which will continue until the end of the study unless the patient has expressly withdrawn their consent to

survival follow-up. Note that the patient may be offered additional tests or tapering of treatment to withdraw safely.

A patient who withdraws consent will always be asked about the reason(s) for withdrawal and the presence of any AE. The Investigator will follow-up AEs outside of the clinical study.

If a patient withdraws consent, they will be specifically asked if they are withdrawing consent to:

- All further participation in the study including any further follow-up (eg, survival contact telephone calls)
- Withdrawal to the use of any samples (see Section 8.8.6)

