### **3.2.3 Adverse Events**

AEs and SAEs will be collected throughout the study, from time of the patient signing the informed consent and 90 days after the last dose of durvalumab. A treatment emergent adverse event (TEAE) is an AE with an onset date or a pre-existing AE worsening following the first dose of study treatment through to 90 days after the last dose of durvalumab.

The Medical Dictionary for Regulatory Activities (MedDRA) (using the latest or current MedDRA version) will be used to code the AEs. AEs will be graded according to the National Cancer Institute Common Terminology Criteria for AEs (CTCAE Version 5.0). The meaning of these categories are as follows:

- Grade 1: Mild AE
- Grade 2: Moderate AE
- Grade 3: Severe AE
- Grade 4: Life-threatening or disabling AE
- Grade 5: Death related to AE

Any TEAE will be included in the AE summaries as detailed in Section 4.5.1.

Missing start and stop dates for AEs will be imputed using the rules described in Section 4.1.3.

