### **3.2.8 Exposure to Durvalumab**

The total (or intended) exposure (weeks) of durvalumab is defined as:

- Total treatment duration (weeks) = Total treatment duration (days) / 7

where:

$$\text{Total treatment duration (days)} = [\text{earliest of (last dose date where dose} > 0\text{mg} + 27 \text{ days, death date, data cut-off date [DCO]-first dose date}]] + 1$$

The actual exposure (weeks) of durvalumab is defined as:

- Actual treatment duration (weeks) = [total treatment duration (days) – total duration of dose delays (days)] / 7.

Dose reductions are not permitted per the CSP for durvalumab and the actual exposure calculation makes no adjustment for any dose reductions that may have occurred.

As patients are scheduled to receive 1500 mg via IV infusion every 4 weeks (28 days), the duration of dose delays is the sum of all individual dose delays as follows:

- Total duration of dose delays (days) = sum of maximum[0, (date of dose [x+1] – date of dose [x] - 28 days)].

If no delays were encountered, the total duration of dose delays would sum up to 0.

According to the protocol, dose delays are defined as doses administered 4 or more days after the target dosing date and reason for dose delay is collected in the CRF based on this definition.

Relative dose intensity (RDI) is the percentage of the actual dose intensity delivered relative to the intended dose intensity through to treatment discontinuation.

RDI is defined as follows:

$RDI = 100\% * d/D$ , where  $d$  and  $D$  are, respectively, the actual and intended cumulative doses delivered up to the date of durvalumab discontinuation or progressive disease or the data cut-off date, whichever occurs earlier.  $D$  is the total dose that would be delivered if there were no modification to dose or schedule.

Percentage intended dose (PID) is the percentage of the actual dose delivered relative to the intended dose through to disease progression.

$PID = 100\% * d_1/D_1$ , where  $d_1$  is the actual cumulative dose delivered up to the earlier of progression (or a censoring event) or the data cut-off date and  $D_1$  is the intended cumulative dose up to the earlier of progression (or a censoring event) or the data cut-off date.  $D_1$  is the total dose that would be delivered, if there were no modifications to dose or schedule.

When deriving actual dose administered the volume before and after infusion will also be considered.

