#### 4.5.5      Exposure

The following summaries will be presented for durvalumab exposure:

- Total (or intended) exposure
- Actual exposure
- Number of cycles received
- Number and Reasons for dose delays of durvalumab. Dose interruptions will be based on investigator initiated dosing decisions.
- Relative dose intensity

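### The AE rate per 100 patient-years in SAP 4.5.1 counts AEs over a longer period than the person-time it divides by

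*SAP*

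**What the plan says.** **Numerator.** SAP 4.5.1 sets a default for all AE summaries: "All TEAEs reported up until 90 days following completion or discontinuation of durvalumab treatment or until the initiation of the first subsequent therapy", whichever comes first, unless a summary states otherwise. SAP 3.2.3 has the same outer limit. A treatment-emergent AE is one with onset, or a "pre-existing AE worsening following the first dose of study treatment through to 90 days after the last dose of durvalumab". Some summaries in the 4.5.1 list do state their own window (one is limited to six months, another ignores subsequent therapy). The bullet that defines the rate does not, so the default applies.

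**Denominator.** The same bullet reads: "The number of patients with an AE in each PT is divided by the sum of the actual exposure to durvalumab (days". It multiplies the result by 365.25 x 100 and calls it an event rate. Its cross-reference is to a Section 0. The only definition of actual exposure is in SAP 3.2.8, under "The actual exposure (weeks) of durvalumab is defined as": total treatment duration minus total dose-delay time. Total treatment duration ends at the earliest of last non-zero dose plus 27 days, death or data cut-off. The delay term is "Total duration of dose delays (days) = sum of maximum" of zero and the days beyond 28 between consecutive doses.

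**Presentation.** SAP 4.1.1 has safety data summarised overall and by radiotherapy cohort. SAP 6 lists no change that bears on this rate.

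**The concern.** A rate per unit of person-time needs events and time taken from the same period. Here there are two gaps. An AE that starts between day 28 and day 90 after the last dose puts a patient in the numerator, but those days are not in the denominator. An AE that starts during a dose delay also counts, but the delay days have been subtracted.

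The second gap does not need long delays. SAP 3.2.8 counts a delay for reporting only from 4 days past the target date, yet its formula removes every day beyond 28, so slippage inside the permitted ±3 days also shortens person-time.

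At stake is the scale of the rate for each preferred term, and how comparable it is between the two cohorts if they differ in treatment length. There is also a labelling problem. Each patient counts once per term and person-time does not stop at first onset, so the result is neither an event rate nor a first-event incidence rate.

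**Working it through.** The SAP gives a formula but no numeric rate, so there is no figure to reproduce. The check applies the definitions in SAP 3.2.3, 3.2.8 and 4.5.1 directly.

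**Days in each period.** Take first dose on Day 1, k doses every 28 days and D delay days in total.
- Last dose day: L = 1 + 28(k − 1) + D
- Total treatment duration: L + 27 = 28k + D
- Actual exposure: 28k + D − D = 28k
- AE window with full follow-up: Day 1 to L + 90 = 28k + 63 + D

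The window exceeds the denominator by 63 + D days.

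**Full follow-up, no new therapy, no delays.**

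| Doses | AE window (days) | Actual exposure (days) | Ratio |
|---|---|---|---|
| 6 | 231 | 168 | 1.38 |
| 10 | 343 | 280 | 1.23 |
| 13 | 427 | 364 | 1.17 |

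**Earlier end of the AE window (6 doses, no delays).** Window ending at last dose + 60 days: 201/168 = 1.20. At + 45 days: 186/168 = 1.11. At + 27 days: 168/168 = 1.00.

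**From days to inflation.** Let r be the post-treatment AE hazard divided by the on-treatment hazard. For an uncommon term with full follow-up and no delays, inflation against the on-treatment rate is (28k + 63r)/28k = 1 + 2.25r/k. The documents do not give r, so these values are assumed:
- r = 0: 1.00 for any number of doses
- r = 0.5: 1.19 (6 doses), 1.11 (10), 1.09 (13)
- r = 1: 1.38, 1.23, 1.17, the ratios in the table

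**Delay days (10 doses, 28 delay days, r = 0).** Let h be the hazard on delay days divided by the on-treatment hazard, also not given. Inflation is (280 + 28h)/280, which is 1.10 at h = 1 and 1.00 at h = 0.

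**On the rate scale (assumed: 10 of 102 patients with the term, equal doses, no delays, full follow-up).** Six doses: 10/(102 × 168) × 36525 = 21.3 per 100 patient-years under the SAP, against 10/(102 × 231) × 36525 = 15.5 over the matched window. Ten doses: 12.8 against 10.4. Thirteen doses: 9.8 against 8.4.

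**Between cohorts (assumed: 6 against 10 doses on average, same on-treatment rate, no delays).** The SAP rate ratio is (1 + 2.25r/6)/(1 + 2.25r/10): 1.00 at r = 0, 1.07 at r = 0.5 and 1.12 at r = 1.

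**The case against.** The strongest reply is that dividing by treatment exposure is a familiar convention, that the bullet says openly that it counts patients and uses actual exposure, and that this is one descriptive column in a single-arm study with no test or decision attached. That stands as an argument about severity. It does not remove the mismatch, because an on-treatment denominator calls for an on-treatment numerator and the SAP does not restrict the numerator.

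The gap is also smaller for many patients. AE counting stops at first subsequent therapy, and patients still on treatment at the primary data cut-off have no tail. The direction can even reverse. A patient who starts new therapy within 27 days of the last dose keeps contributing person-time after AE counting has stopped. So does one who withdraws consent in that time, since Protocol 7.3 says "Patients who withdraw consent for further participation in the study will not receive any further durvalumab or further study observation" (survival follow-up aside). The ratios 1.17 to 1.38 therefore describe fully followed patients, not the trial as a whole.

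Two stronger readings are tempting, and the documents support neither.
- A reader might take the constant-hazard figures as a ceiling, because Protocol 4.2.1 says that "the majority of imAEs with durvalumab occurred during the first 6 months of treatment" in an earlier study. That sentence concerns immune-mediated AEs only, by time since treatment start. It does not compare hazards after and during treatment. For a patient who stops after two doses, the post-treatment window falls inside those first six months. It cannot bound r at 1.
- A reader might infer that the delay effect inflates the rate whatever the hazards. It does so only if AEs start on delay days. The 1.10 assumes the full on-treatment hazard on those days.

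The Section 0 reference may be no more than a broken field and carries no weight in the argument.

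**Conclusion.** The mismatch is in the text, and nothing elsewhere in the SAP repairs it. Followed as written, the rule gives a mis-scaled rate. The structural gap is up to 63 days per patient plus all delay days, or 1.17 to 1.38 in window-to-exposure days for 13 down to 6 doses with full follow-up, no new therapy and no delays. How far the reported rate moves depends on the post-treatment hazard, the hazard on delay days, the doses received and the delay totals, none of which the documents give. With no post-treatment AEs and no delays there is no inflation.

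Severity is minor. One descriptive column, shown overall and by cohort, is affected. A reader might extend the point to the main safety result, but the number and percentage of patients with each AE do not use person-time, and the primary endpoint in SAP 4.3 is a proportion with an exact interval.

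**What to change.** In SAP 4.5.1, use one period for both parts of the rate.

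**Preferred.** Replace actual exposure with person-time from first dose to the earliest of last dose + 90 days, first subsequent anticancer therapy, death, withdrawal of consent or last AE assessment, or data cut-off, without subtracting dose delays. Last AE assessment is the workable end point for patients who drop out of contact, because Protocol 7.2 declares loss to follow-up only at study completion. The numerator then equals the n in the same row. The rate describes the whole window, so cohorts with different treatment length can still differ when r is below 1. For 6 against 10 doses, [(168 + 63r)/231]/[(280 + 63r)/343] is 0.95 at r = 0.5 and 0.89 at r = 0.

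**Alternative.** Count only AEs that start within total treatment duration (SAP 3.2.8) and divide by that duration without subtracting delays. Add a footnote that this numerator differs from the n (%) shown and omits AEs that start later in the 90-day window.

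**Label, for either.** Call the result an exposure-adjusted rate of patients with the event.

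**Cost.** One SAP sentence and one derived person-time variable. The alternative can reuse the "Total (or intended) exposure" already planned in SAP 4.5.5, but only if no further end points such as subsequent therapy or withdrawal are added. No new data are collected.

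**Editorial.** Point the Section 0 reference to 3.2.8, and note that 3.2.8 defines actual exposure in weeks while 4.5.1 uses days.

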2.3.2.1 Durvalumab

Risks with durvalumab include, but are not limited to, diarrhea/colitis, pneumonitis/ILD, endocrinopathies (ie, events of hypophysitis/hypopituitarism, adrenal insufficiency, hyper- and hypothyroidism, type I diabetes mellitus, and diabetes insipidus), hepatitis/increases in transaminases, nephritis/increases in creatinine, pancreatitis/increases in amylase and lipase, rash/dermatitis, myocarditis, myositis/polymyositis, infusion-related reactions, hypersensitivity reactions, pancreatitis, serious infections, and other rare or less frequent inflammatory events including neuromuscular toxicities (eg, Guillain-Barre syndrome, myasthenia gravis).

For information on all identified and potential risks with durvalumab, please always refer to the current version of the durvalumab IB.

In monotherapy clinical studies, AEs at an incidence of > 20% include events such as fatigue, cough, decreased appetite, dyspnea, and nausea. Approximately 10% of patients discontinued the drug due to an AE. In the PACIFIC Study in patients with Stage III NSCLC following cCRT, AEs (all causality) experienced during the study with an incidence of > 10% (durvalumab vs

placebo) were cough (35.4% vs 25.2%); fatigue (23.8% vs 20.5%); dyspnea (22.3% vs 23.9%); radiation pneumonitis (20.2% vs 15.4%); diarrhea (18.3% vs 18.8%); pyrexia (14.7% vs 9%); decreased appetite (14.3% vs 12.8%); nausea (13.9% vs 13.2%); pneumonia (13.1% vs 7.7%); pneumonitis (12.6% vs 7.7%); arthralgia (12.4% vs 11.1%); pruritus, rash and upper respiratory tract infection (12.2% each vs 4.7%, 7.3% and 9.8%, respectively); constipation (11.8% vs 8.5%); hypothyroidism (11.6% vs 1.7%); headache (10.9% vs 9.0%); asthenia (10.7% vs 13.2%); and back pain (10.5% vs 11.5%). Combined events of pneumonitis or radiation pneumonitis occurred in 33.9% vs 24.8% of patients, including CTCAE Grade 3 pneumonitis or radiation pneumonitis in 3.4% vs 2.6% of patients; no patients in either treatment group reported Grade 4 events of pneumonitis or radiation pneumonitis.

Please see the current version of the IB for a detailed summary of the monotherapy data including AEs, serious adverse events (SAEs), and CTCAE Grade 3 to 5 events reported across the durvalumab program.

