4.2.4 Rationale for treatment duration

Treatment in this study will continue for 12 months or until RECIST 1.1-defined PD and Investigator determination that the patient is no longer benefiting from treatment with IP, or until another discontinuation criterion is met (see Section 7.1). This guidance is supported by data from the PACIFIC Study, in which patients were treated for up to 12 months with durvalumab, and no new safety signals were observed after 6 months of treatment (Antonia et al 2017). The median duration of treatment in the PACIFIC Study was 40.1 weeks (range, 1 to 54) in the durvalumab group, suggesting that durvalumab treatment was tolerable in this patient population (Antonia et al 2018). Numerous Phase III studies are currently evaluating durvalumab treatment until PD for patients with a variety of malignancies. Although the results of these studies are not yet available, no new safety signals have been identified as a result of the longer duration. In order to balance the patient burden associated with monthly visits until disease progression with the potential for additional clinical benefit with prolonged treatment duration, durvalumab will be administered for 12 months in this study.

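### The SAP's adverse event rate per 100 patient-years divides a once-per-patient count by everyone's whole exposure, so it is neither an event rate nor a first-event incidence rate, and its net error can go either way

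*SAP*

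**What the plan says.** SAP 4.5.1 (Adverse Events) adds a rate to the all-AE summary by SOC and PT: "This summary will include an AE event rate (per 100 patient years) for each PT". The definition follows: "The number of patients with an AE in each PT is divided by the sum of the actual exposure to durvalumab (days"), taken over all patients. The scaling is then given: "This is multiplied by 365.25 x 100 to create an event rate per 100 patient years".

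Two other provisions matter.

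- **Numerator window.** SAP 4.5.1 includes "All TEAEs reported up until 90 days following completion or discontinuation of durvalumab treatment or until the initiation of the first subsequent therapy", whichever is first.
- **Denominator window.** SAP 3.2.8 (Exposure to Durvalumab) ends total treatment duration at the earliest of the last non-zero dose plus 27 days, death or data cut-off. Actual exposure is then "total treatment duration (days) – total duration of dose delays (days"), divided by 7.

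Neither section ends a patient's person-time at the first onset of the PT. SAP 4.5.1 refers the reader to a Section 0 for the exposure definition. The definition is in 3.2.8, where actual exposure is in weeks, whereas the rate formula calls for days.

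**The concern.** A patient who has had the PT cannot add to the numerator again but goes on adding days to the denominator. An event rate would count every episode. A first-event incidence rate would stop the clock at onset. The SAP's figure does neither, yet it is labelled an event rate.

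It is the only exposure-adjusted AE figure I can find in the unredacted plan of a trial whose main purpose is safety. The part of the error that comes from time after onset grows with incidence, so it compresses differences between common and rare PTs. SAP 4.1.1 summarises safety data by radiotherapy cohort, so any cohort difference in incidence would be compressed too. A reader who compares the column with a properly defined rate from another study would not be comparing like with like.

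**Working it through.** The plan states no expected rate, PT incidence or onset time for this table, so there is no figure of its own to reproduce.

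**Inputs**

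- Incidence *p*: the PACIFIC durvalumab figures in Protocol 2.3.2.1 serve as proxies. Examples are back pain 10.5%, "radiation pneumonitis (20.2% vs 15.4"%), fatigue 23.8% and cough 35.4%.
- Exposure *T*: Protocol 4.2.4 states "The median duration of treatment in the PACIFIC Study was 40.1 weeks (range, 1 to 54) in the durvalumab group". I use 40.1 × 7 = 280.7 days as a common proxy; the SAP gives no expected exposure.
- Excess of the numerator window: 90 - 27 = 63 days, counting from the last dose.
- Hazard shape and onset time: assumptions, not in the documents.

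**Step 1: time after onset, taken alone.** With constant hazard λ and common exposure, p = 1 - exp(-λT). The SAP rate is p/T and the first-event rate is λ = -ln(1-p)/T. The ratio is p/(-ln(1-p)).

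| p | -ln(1-p) | ratio | shortfall |
|---|---|---|---|
| 10% | 0.1054 | 0.949 | 5.1% |
| 10.5% | 0.1109 | 0.947 | 5.3% |
| 20% | 0.2231 | 0.896 | 10.4% |
| 23.8% | 0.2718 | 0.876 | 12.4% |
| 35.4% | 0.4370 | 0.810 | 19.0% |

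A 10% shortfall needs an incidence of about 19%. Of the 19 PACIFIC AEs listed above 10% in Protocol 2.3.2.1, only cough, fatigue, dyspnea and radiation pneumonitis reach it.

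More generally the shortfall is p × f, where f is the mean share of exposure left after onset among cases. With f = 0.75 it is 15.0% at p = 20% and 26.5% at 35.4%. With f = 0.25 it is 5.0% and 8.8%.

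**Step 2: compression.** Suppose two cohorts have equal exposure and incidences of 20% and 35.4%. The first-event rate ratio is 0.4370/0.2231 = 1.96. The SAP's ratio is 0.354/0.20 = 1.77. Between PTs, cough relative to back pain is understated by 1 - 0.810/0.947 = 14%.

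**Step 3: add the window mismatch.** If events are counted over T + 63 = 343.7 days, the matched first-event rate is -ln(1-p)/343.7. The ratio in Step 1 is multiplied by 343.7/280.7 = 1.224.

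| p | SAP rate against matched first-event rate |
|---|---|
| 10.5% | +15.9% |
| 20% | +9.7% |
| 23.8% | +7.2% |
| 35.4% | -0.8% |

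A simulation varied the pattern: up to 13 four-weekly doses, mean actual exposure about 38 weeks, constant or front-loaded hazard, 0 to 100% of patients starting subsequent therapy within the 63 days, and (with no subsequent therapy) delays of 0 or 5%. For incidences of 10.5-35.4% the net error ran from about +20% to -17%. The high end comes from delays with no subsequent therapy. The low end comes from early onset with all patients starting subsequent therapy.

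**Step 4: stopping the clock without matching the windows.** If person-time ends at onset but still stops at the SAP's exposure end, the ratio to the true rate is p/(1 - exp(-λT)), with λ = -ln(1-p)/343.7. For cough, λT = 0.4370 × 280.7/343.7 = 0.357, so the ratio is 0.354/0.300 = 1.18. Cough would move from about -1% to about +18%. The two parts must therefore be corrected together.

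**The case against.** The strongest reply is that the formula is fully stated, sits beside n and % for every PT, and is purely descriptive. The study is single-arm, no rate comparison or test is specified, and the primary endpoint (SAP 4.3) is a proportion with a Clopper-Pearson interval. SAP 4.5.1.1 also summarises time to first onset directly for events of special or possible interest. All of that stands, and it limits the weight of the point. It does not rescue the label, because a count of patients over whole exposure is not an event rate under any of the plan's definitions.

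A reader might go further and infer that the reported rates of common AEs will be 10-30% too low. The documents do not support that, for three reasons.

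- The unmatched windows push the figure up, and for many PTs above 10% incidence they outweigh the loss from time after onset.
- Even alone and under a constant hazard, the shortfall reaches 10% only at about 19% incidence, and 30% only above 50%. Protocol 2.3.2.1 lists no PT that high.
- Larger shortfalls need early onset with long exposure afterwards. Protocol 4.2.1 says most immune-mediated AEs in PACIFIC fell in the first 6 months, but that does not fix *f*. An AE that stops dosing ends exposure soon afterwards, and delay days are subtracted. So it is not shown that events such as pneumonitis (12.6% in PACIFIC) are the worst affected.

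**Conclusion.** The definition and label are wrong as written, and both are worth correcting. The certain part is structural: a once-per-patient numerator over person-time that is not stopped at onset, with different windows above and below the line. The component sizes in Step 1 assume a constant hazard and common exposure. The net range also rests on PACIFIC exposure and incidence as proxies and on assumed onset, delay and subsequent-therapy patterns. No direction of net bias should be claimed. The compression between PTs is firmer: with common exposure and constant hazard the window factor cancels from the comparison. The consequence is confined to one descriptive column, so this is a desirable clarification rather than a threat to the trial's conclusions.

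**What to change.** In SAP 4.5.1, define for each PT the number of patients with a first event divided by person-time from first dose to the earliest of: first onset of that PT, 90 days after the last dose, start of subsequent anticancer therapy, death, or data cut-off. Do not subtract delay days. Label the column as an exposure-adjusted first-event incidence rate per 100 patient-years.

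If an event rate is intended, divide all episodes by total time in that same TEAE window and say so.

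In the same edit, change the reference to Section 0 to 3.2.8 (or to the new person-time definition) and reconcile days with weeks. The 365.25 multiplier needs days, and weeks would inflate the rate sevenfold.

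The cost is a few SAP sentences and, for the first-event version, a PT-specific denominator in the program. Onset dates are already collected and imputed under SAP 4.1.3. The denominator will differ by PT, and reported rates will change modestly.
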